The trainee is expected to identify a coloured pushpin (e.g. red), grasp it by the head with grasping forceps (Johans) using their NDH, then transfer the pin to their DH and grasp the pin by its tail using curved forceps like Maryland. The pushpin then needs to be placed in the corresponding disc of the same colour correctly before moving on to the next coloured pushpin. Correct placement is achieved when the trainee has placed the pushpin (either its head or tail) in the respective disc. Trainee can use both hands to stop the pin from falling out. The trainee will continue until the 3 minutes time limit is reached or all the 6 pins have been correctly placed. If a pin is dropped the trainee can re grasp it if possible or choose to use the second pin of the same colour provided it is still in endoscopic view. Number of dropped pins will be recorded. If 3 minutes have lapsed and the task is incomplete, then the total number of pins positioned will be counted. This task will be repeated 3 times and scores for each run will be recorded on validated evaluation sheets (**Appendix 8**). To avoid memory effect the colour sequence of targets will be changed each round. The same 3 sequences will be used for all trainees throughout the testing phase (**please see the end of appendix 7**).

Task 4 - Suturing and knot placement

All trainees will be shown a video demonstration of laparoscopic suturing and intra corporeal knotting.

A Suturing and knot tying Training and Testing method (SUTT1) foam pad will be used for assessment of suturing and knot placement (Figure 2). This has 5 rows of dots. For this task the top 4 rows are used and the 5th row is disregarded.

Figure 2. SUTT1 foam pad for assessment of suturing and intra corporeal knot tying. It contains 5 rows of large black dots placed about 10mm apart.

The facilitator will set up the SUTT1 model inside a Szabo box trainer and insert 2 lateral ports approximately half way down the box. This is to allow easy access to the foam pad. A 10mm 0 degrees camera will be introduced through the central port and held in an optimal position for this task by the facilitator or according to the trainee's instructions. The trainee will be given standardised instructions and a video demonstration on how to perform this task. **(Appendix 7)**.

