Trainees will be expected to place interrupted sutures between two dots and perform 4 intra corporeal knots with 3 throws. They will be instructed to place sutures between the two dots along the first 4 rows on the foam pad. The trainee is not expected to use the 5th row at the bottom of the foam pad. A total of 15 minutes will be allowed for this task and the time taken to complete 4 sutures and 4 knots if performed will be recorded. If the trainee runs out of time, then total number of sutures +/- knots performed within the 15 minutes will be recorded. At the completion of the tasks, each foam pad will be labelled with the trainee's study number and collected. The quality of suturing and knot will be assessed after completion of the task using validated SUTT scoring system by two independent assessors **(Appendix 9)**.

Measurement of EMG and EEG

Musculoskeletal and cognitive fatigue will be tested using electromyography (EMG) and electroencephalography (EEG) respectively in a sub set of trainees as described earlier. They will be fitted with EMG and EEG electrodes as per the protocol and this data will be collected for round 2 of tasks 1-3 and throughout the duration of the suturing task 4. As the equipment is wireless, it is anticipated that the trainee's freedom of movement will not be affected by it. EMG will be measured by placing wireless electrodes over arms, neck and upper and lower back muscles **(Appendix 10)** and EEG will be recorded using wireless electrodes over the scalp using a validated protocol **(Appendix 11)**.

Location and timescale for experiments

We have opted to conduct these tasks in a large seminar/conference room to minimise any potential pressure on performance of another colleague. We are restricting the number of trainees to a maximum number of 6 per each run. We will conduct these tasks over 3 weekends (2 consecutive weekends and one weekend 3 weeks later). The rationale behind this is to increase the chances of recruiting volunteers who may be restricted otherwise by on-call commitments or might be away on leave.

Choice of location will be between Royal Blackburn hospital and Manchester based hospitals.

Outcome measures

The primary outcome measure:

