Runs	Time required for inserting 6 cylinders OR 3 minutes	No of cylinders placed in 3 minutes	No of dropped objects
1	: :		
2	: :		
3	: :		

Task 3: Bimanual co-ordination (BMC)

Runs	Time required for positioning 6 pins OR 3 minutes	No of pins placed in 3 minutes	No of dropped objects
1	: :		
2	: :		
3	: :		

Appendix 9

Scoring sheets for laparoscopic suturing and knot quality:

European
 +theAcademy of
 Gynaecological
 Surgery

SUT+T1 EVALUATION

RESULT			
TIME:	:	:	max 15 min.
DOT:	0	1	2 3 4 5 6 7 8 9 10
CORRECT STITCH:	0	1	2 3 4 5
KNOT:	0 - 2	TRAUMA:	0 1 2

1) TIME

Time maximum - 15 minutes

2) DOT 0-1-2-3-4-5-6-7-8-9-10

To count dots through which the thread is passed correctly.

Dot may be counted when the stitch (thread) is entered in any point of the dot (when the thread is visually in contact with any part of the dot)
 Incorrect dot (not to be counted) is considered when the stitch is passed obviously out of the knot

3) CORRECT STITCH 0 – 5

The thread is passed correctly through **both dots**

4) TRAUMA

The damage of the suturing pad

0 = minimal, no damage | 1 = moderated damage | 2 = heavy damage

5) KNOT 0 – 1 - 2

Flat knot and two additional half knot

2 = knot is correct and tied | 0 = all the rest

Trauma

0: No damage, up to 4 needle puncture marks, no excavation, or exposed foam irrespective of the size of defect.

1: Between 5 and 8 needle puncture marks, defect in foam pad of less than 5mm or extent of trauma more than grade 0 but less than grade 2.

2: More than 8 needle puncture marks, Underlying foam exposed, defect in foam pad of 5mm or more, excavation and cavity formation.

Knot quality:

2: square knot, 3 throws and flat.

0: any of the above absent.

Knot quality should be assessed for each knot. Overall score for this section (knot quality) is the sum of all knots quality scores.

Appendix 10

Electromyography (EMG) protocol

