The aim of this task is to perform 4 interrupted sutures and knots using correct needle handling and intra-corporeal knot tying techniques.

Remove the LASTT model along with its inserts from the box trainer.

A Suturing and knot tying Training and Testing method (SUTT1) foam pad will be used for assessment of suturing and knot placement (Figure 2). This has 5 rows of dots. For this task the top 4 rows are used and the 5th row is disregarded.

[figure not shown]

Figure 2. SUTT1 foam pad for assessment of suturing and intra corporeal knot tying. It contains 5 rows of large black dots placed about 10mm apart.

The suturing pad is affixed on an A4 card labelled SUTT-1. This card is to be secured on to a large black foam base. This foam base has 2 raised edges near the top.

Align the top of A4 SUTT-1 card with the top ridge on this foam base and then secure it on to the foam base using 6 pins (3 pins along each long edge of A4 card).

Attach the large foam base to the floor of the Szabo box trainer using 4 Velcro strips at the four corners. The purpose of this is to prevent any potential movements of the suturing pad/base during the suturing task.

Cut 6 Vicryl 2.0 sutures to a length of 20cm.

As the facilitator you are expected to insert the 0 degrees camera through the central port in the middle of the box trainer. Insert two 5mm lateral ports (left and right) halfway down the box.

Request the trainee to read the instructions and then show them the suturing demonstration video.

Check trainee's understanding of the task.

The trainee is required to perform 4 interrupted sutures by taking a needle bite through the black dots in a horizontal plane. Please instruct the trainee to use the first 4 rows on the suturing pad and leave the 5th row.

The trainee is expected to pass the suture by entering and exiting precisely within the black dots and perform intra-corporeal knot with 3 throws. They should then cut the excess suture using laparoscopic scissors leaving behind a tail of approx. 1-2cm. This process can then be repeated along the 4 rows to perform a total of 4 sutures and 4 knots.

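### Appendix 9 gives two incompatible ranges for the Task 4 knot score: a single printed field of 0-2, and a summing rule that reaches 8 for four knots

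*Protocol*

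**What the plan says.** The Task 4 section of the protocol and the assessor information in Appendix 13 agree on the task. On the pad: "This has 5 rows of dots. For this task the top 4 rows are used and the 5th row is disregarded". On the work: "They will be instructed to place sutures between the two dots along the first 4 rows on the foam pad", and "This process can then be repeated along the 4 rows to perform a total of 4 sutures and 4 knots". Two independent assessors score the pad after the session, using the sheet in Appendix 9.

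That sheet treats the knot in three ways:

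- The result box has one knot field for the pad, with the range 0 to 2.
- Item 5 is headed with the levels 0, 1 and 2, but its key has only two: "2 = knot is correct and tied | 0 = all the rest".
- The notes at the end repeat the two-level key (2 or 0), ask for an assessment of every knot, and add: "Overall score for this section (knot quality) is the sum of all knots quality scores".

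The Outcome measures section lists Task 4 under the primary outcome. It names the number of sutures, the correct knots and the extent of trauma as what is recorded. It does not say on which scale the knots are reported.

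**The concern.** The result field and the summing rule on the same sheet cannot both be followed for a pad with two or more correct knots. An assessor who keeps to the printed range enters at most 2. One who follows the notes enters up to 8. The undefined level 1 adds to the uncertainty, because someone giving a single overall rating to a pad with some good and some bad knots might choose it.

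Knot quality is a component of Task 4, which is listed under the primary outcome, and the sheet is what should make the two assessors' scores comparable. Appendix 8 has evaluation tables for Tasks 1 to 3 only, so no other Task 4 form in the protocol settles the matter. The phrase in Outcome measures does not settle it either, since a number of correct knots is naturally a count from 0 to 4, a third possible scale.

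**Working it through.** **Inputs**

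- Rows on the pad: 5; rows used: 4 (Task 4 section; Appendix 13).
- Dots per row: 2, one stitch per row (Task 4 section).
- Knots required: 4 (Task 4 section; Appendix 13).
- Score per knot: 2 or 0 (Appendix 9, item 5 and closing notes).
- Overall knot score: sum over knots (Appendix 9, closing notes).
- Printed ranges: dots 0-10, correct stitches 0-5, knot 0-2 (Appendix 9).

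**Where the printed ranges come from**

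- Dots: 5 rows × 2 = 10. This reproduces the printed maximum.
- Stitches: 5 rows × 1 = 5. This also reproduces it.
- Knot: one knot × 2 = 2. The printed 0-2 is reproduced only as the scale for one knot. As an overall score it matches neither four knots (4 × 2 = 8) nor five (5 × 2 = 10).

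**The task as set (four rows)**

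- Dots: 4 × 2 = 8.
- Stitches: 4.
- Knot sum: 4 × 2 = 8, in steps of 2.

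**Knot result by number of correct knots**

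With k correct knots, the sum is 2k and the count is k. The sum fits the printed field if 2k ≤ 2. The last two columns show how one overall entry of 0-2 might be made. Both are assumptions, since the sheet defines neither: all-or-none (2 only if all four knots are correct), and capped (the smaller of 2k and 2).

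| Correct knots k | Count | Sum 2k | Fits 0-2 field | All-or-none entry | Capped entry |
|---|---|---|---|---|---|
| 0 | 0 | 0 | yes | 0 | 0 |
| 1 | 1 | 2 | yes | 0 | 2 |
| 2 | 2 | 4 | no | 0 | 2 |
| 3 | 3 | 6 | no | 0 | 2 |
| 4 | 4 | 8 | no | 2 | 2 |

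Three of the five possible totals (4, 6 and 8) lie outside the printed field. At four correct knots the sum is 8 against an entry of 2, a ratio of 8/2 = 4. A single entry also loses information: the all-or-none reading puts pads with 0 to 3 correct knots together at 0, and the capped reading puts pads with 1 to 4 together at 2.

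The count and the sum differ only by a factor of 2, so either can be recovered from the other if each knot's score is written down. Neither can be recovered in general from one entry between 0 and 2.

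**The case against.** The strongest reply is that the rule is there. The closing notes say to score each knot and add the scores, and the key is worded for one knot, so 0-2 can be read as the per-knot scale. Since everything that is not a correct knot scores 0, no knot could earn a 1. On this view an assessor arrives at 2 instead of 8 only by overlooking an instruction on the same sheet. Pads are labelled and kept, so such a discrepancy would be visible and the pad could be rescored. The sheet's layout was also flattened when its text was extracted, so the look of the knot entry is not certain.

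Most of this stands as a limit on the practical risk. It does not remove the conflict: the result box shows a range that the stated total exceeds, and level 1 is offered without a meaning.

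A reader might infer more from this sheet than the protocol supports:

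- **That the dot and stitch ranges also make assessors disagree.** The sheet does print "2) DOT 0-1-2-3-4-5-6-7-8-9-10" and stitches to 5, against reachable maxima of 8 and 4. But both are plain counts with a stated rule, for dots "To count dots through which the thread is passed correctly". Two people counting the same four rows get the same number whether the printed scale stops at 8 or at 10.
- **That a stitch on the fifth row would earn credit.** The score sheet does not repeat the exclusion, but the Task 4 section and the assessor information both say "For this task the top 4 rows are used and the 5th row is disregarded", and trainees are told to leave that row.
- **That a flawless pad would be marked down as 8 of 10 or 4 of 5, or set against scores from the five-row version.** The protocol expresses no score as a share of the printed maximum and plans no such comparison.
- **That the two assessors' conflicting entries would be averaged, or would create a difference between specialties.** The protocol specifies no averaging. A specialty difference would need the readings of the form to be spread unevenly across the specialties, and nothing in the text says so.

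**Conclusion.** The knot entry in Appendix 9 is wrong as written. One field of 0-2, with an undefined level 1, sits beside a rule whose total for the required four knots runs from 0 to 8. The two readings agree for a pad with no correct knot. With two or more correct knots the summed total cannot be entered in the printed field, and at four correct knots the two readings are 2 and 8. The Outcome measures wording leaves a 0-4 count as a further possibility.

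This is an internal inconsistency on a form that feeds a component of the primary outcome. It rests on two assumptions: that the result box holds one knot entry for the whole pad, as the extracted text shows, and that an assessor might follow that box over the notes. The explicit summing rule makes the second less likely, so the practical risk is modest. The unused top values for dots (9 and 10) and stitches (5) are untidy but harmless to agreement between assessors.

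**What to change.** 1. In Appendix 9, replace the single knot field with four boxes, one per knot, each 0 or 2, followed by a total of 0-8.
2. Delete level 1 from the heading of item 5.
3. In Outcome measures, state whether the Task 4 knot result is the 0-8 sum or the 0-4 count of correct knots.
4. As tidying only, print the dot range as 0-8 and the correct-stitch range as 0-4, and label both as covering rows 1 to 4.

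The cost is one revised form and one sentence. Nothing changes for trainees or on the study day, because the pads are labelled, collected and scored afterwards. Any pad already scored on the present sheet can be scored again from the stored pad.

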The task will be set up by the facilitator and will give the trainee standardised instructions and a short demo video on how to perform this task (**Appendix 7**). The task begins when the trainee inserts the camera to find the character on the first target (e.g. **1**), zoom in and identify the small size character (e.g. **a**) located next to it. Before they can proceed to the next target, the facilitator needs to confirm that they are happy with the identification and placement of the small character by saying "next". Trainee can demonstrate this by placing the target in the circle on the screen and reading it out. Trainee can then navigate the camera to find the next target on the LASTT model which in the above example will be large character '**A**', then zoom in to find the small character next to it, put the small character in the circle on the screen and read it out. They can then move on when indicated by faculty as ok to do so. Trainee can then continue until they find the 14th target "**N end**" which completes the task. Please see figure 1 for an example. The facilitator will record the trainee's study number (badge number) and time taken to identify 14 targets. A time of 2 minutes and 30 seconds is considered as ideal for completion of this task. If trainee exceed this time then it will incur a penalty. For every

30 seconds they exceed beyond 2 minutes and 30 seconds, 1 target will be subtracted from the total number of targets they have found. The penalty column does not need to be completed at the time of assessment and can be worked out retrospectively. Furthermore maximum time allowed for this task is 5 minutes and if all 14 targets have not been identified within 5 minutes then the trainee is encouraged to move on to the second sequence of this task, i.e. round 2. The assessor will be required to record the last target found on the evaluation sheet if 5 minutes limit is reached and the task is still incomplete. The rationale for the 5 minute cap is to minimise fatigue. This task will be repeated 3 times and above data will be recorded on the evaluation sheet (**Appendix 8**). To avoid memory effect the sequence of targets will be changed each round so that there are 3 different sequences to find. The same 3 sequences will be used for all trainees throughout the testing phase (**please see the end of appendix 7**).

Task 2 - Hand eye co-ordination (HEC)

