To assess HEC, trainees are assessed on their ability to transfer objects as well as navigate the camera. The trainee is expected to use the dominant hand (DH) to hold grasping forceps and non-dominant hand (NDH) to hold the camera. The LASTT model will be used to assess this.

The facilitator will set up the Szabo box trainer for this task. Coloured cylinders will be placed (10 × 4-mm open cylinders) in a circular style in a vertical upright position around the “+he academy...” sign on the LASTT model. There will be 2 cylinders of each colour in case one is dropped out of view. Corresponding coloured targets, i.e. nails (10 × 1 mm) will be located in easy view on the LASTT model. Facilitator will place 1 lateral port so that the coloured cylinders and LASTT model can be comfortably reached. The facilitator will give standardised instructions and show a standardised demonstration video on how to perform this task (**Appendix 7**).

The trainee is expected to insert the 10mm 0 degrees camera through the central port of Szabo box trainer. The time starts when the trainee inserts the grasper through the lateral port and the grasper comes into endoscopic view. The trainee is expected to identify a coloured cylinder (e.g. green), grasp it with Maryland forceps using their DH and transfer it to the corresponding coloured nail whilst using NDH to drive the camera. Once the cylinder is correctly placed over the pin, the trainee can proceed to the next coloured cylinder and continue until 3 minutes have elapsed or all the 6 cylinders have been transferred. If a cylinder is dropped the trainee can re grasp it if possible or choose to use the second cylinder of the same colour provided it is still in endoscopic view. All grasped then dropped cylinders will also be recorded. This task will be repeated 3 times and scores for each run will be recorded on the task evaluation sheets (**Appendix 8**). The time taken for the trainee to transfer 6 objects correctly will be recorded (if completed in 3 or less minutes) or if the task is incomplete in 3 minutes, then the total number of cylinders transferred will be counted. To avoid memory effect the colour sequence of targets will be changed each round. The same 3 sequences will be used for all trainees throughout the testing phase (**please see the end of appendix 7**).

Task 3 - Bimanual co-ordination (BMC)

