We believe consent is a dynamic process and it will start when we make initial contact with the trainees and consultants via email. They will be provided with participant information sheet including contact details of the research team. In part 2 consent will be confirmed in writing for both the laparoscopic tasks and EMG/EEG recordings. All efforts will be made to communicate appropriately including facilitating access to translational and interpretation services if needed. All our prospective trainees are likely to be fluent in English so we do not anticipate English language barriers.

Risks, burdens and benefits

The study does not involve any invasive procedures/tasks. It does not raise any issues which may be upsetting to the trainees.

Muscular and cognitive fatigue will be measured using wireless sensors over head, shoulders, arms, upper and lower back. These are painless, discreet and unlikely to impede any freedom of movements.

The researcher responsible for applying these electrodes is a male surgeon. If a female trainee prefers the electrodes to be applied by a female staff then we will respect such wishes. We have trained female members of the research team to be able to undertake this task.

Four laparoscopic tasks are assessed using simulator boxes with inanimate models. Study duration will be kept to a minimum to avoid fatigue and refreshments will be provided throughout.

To minimise pressure on trainees, the study will be conducted over a weekend and away from their workplace. We will try to ensure that there is plenty of physical space for each trainee and their facilitators to minimise performance related pressure on each other. The environment will be kept comfortable and constant to minimise adverse effects on performance. If they want to have a different facilitator because they may know or feel uncomfortable with them then they can discreetly request this from a member of the research team. They don't have to give a reason.

We will try to minimise any burden on trainee by providing the following: Ensuring access to lavatory facilities, refreshments, lunch and in inconvenience allowance aimed at covering their travel and parking costs.

The risk of covid 19 transmission is an on-going issue. We will adhere to local guidelines regarding reducing transmission, wear face covering, maintain a distance and have ample hand sanitising facilities in place. We

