Similar to the EMG data capture, EEG data will also be collected during the surgical task. The skin site on the head will be prepared as previously described before the electrode gel and electrode cap are applied. Electrodes will be placed over the cortex using an 8-channel electrode montage to record ongoing EEG oscillations during surgery. Electrodes will be positioned according to the 10-20 international electrode placement system. The main EEG channels of interest will be positioned over the occipital and parietal cortex, namely electrode locations O1, O2, P3, P4, P7, P8 where maximal alpha activity can be detected. A wireless EEG system has been selected so that it is minimally invasive and does not interfere with movement during the task.

Data will be collected and analysed using Enobio 8 5G (Neuroelectronics, Cambridge, MA, USA) using standard referencing, sampling, filtering and smoothing technique. We will compare peak alpha power, and alpha spindle duration and amplitude between groups. Changes in EEG power spectra, specifically in the alpha frequency band, will be used to monitor alertness. We will also be able to identify how alertness changes over time during surgery through the EEG power spectra.

Figure: Example wireless EEG sensor placement

Appendix 12

Equipment

6 stack systems (monitor, 10mm optic (0 and 30 degrees, light))

Laparoscopic 5mm ports x2, 10mm port x1

Tissue grasping forceps (Johans)

Kelly/Maryland dissecting forceps

Needle holders (right and left)

Laparoscopic scissors

Vicryl 2.0 sutures each one cut to 20cm in length.

SUTT1 foam pads

Wooden LASTT model with its inserts

Stop-watch

Weighing scale

Measuring tape for height

Appendix 13

Assessor Information

An assessor will be allocated to each trainee who will mount the relevant inserts into LASTT model, replace the LASTT model with SUTT suturing pad and set up equipment as in Appendix 9.

They will provide the trainee with standardised instructions before each task and discreetly fill out the scoring sheets. The assessors will not give any performance feedback although they can clarify the instructions as many times as necessary on the trainee's request. They will use the stopwatch and keep the trainee updated with how much time they have used up.

Task 1:

The aim of the first exercise is to navigate the 30° camera to locate all targets in the shortest amount of time.

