Place the LASTT model in the box such that the top edge of this box is lined up with the second white pin along the side of box trainer. Put the inserts as per sequence 1.

A 10mm and 30 degrees camera is used. It is to be inserted through the most proximal central port on the Szabo box trainer. Request the trainee to read the instructions and then show them the demonstration video.

Check trainee's understanding of the task.

On the LASTT model there are 14 targets. Each target consists of a large character and a small character (numbers and alphabet letters).

The task time begins when the trainee inserts the camera to find the first target. The small character on that target indicates their next target.

The first target is always '1a'. Trainee starts their search by locating the first target "1a". The figure below is an example of what the first target looks like.

Large character '1' corresponds to the starting character.

Small character 'a' corresponds to the next character to find which will appear as a large character on the subsequent target.

Once the small character is found, trainee needs to zoom in and place the small character in the circle on the screen. If you approve that the entirety or boundaries of the small character is placed in the circle on the screen then indicate that they can move on to next target by saying 'next.' The trainee should now navigate the camera to find capital 'A' on the next target, then zoom in, find the small character next to it

and place it in the circle on the screen and then move on. The trainee can continue until all 14 characters have been found indicated by finding 'Nend'. This completes the task.

Record the time taken to find 14 targets for each round. Ideal time for completing this task is 2 minutes and 30 seconds. However we are allowing a maximum time of 5 minutes for its completion. If trainee is unable to complete the task within 5 minutes, then stop the trainee at that point and record the last target they found; e.g. Mq.

Now change the inserts for round 2 using sequence 2 and repeat above. Record the same data as above before proceeding to round 3 using sequence 3. Once this round is completed, record the above data and move the trainee on to task 2.

Exercise 2: Hand-eye Coordination

The aim of this exercise is to test the trainee's ability to navigate the camera with their non-dominant hand and to simultaneously handle the forceps with their dominant hand.

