The LASTT model stays in position as per task 1.

Put the coloured inserts as per sequence 1 for task 2 in the LASTT model.

A 10mm and 0 degrees camera is used for this task. The camera is to be inserted through the most proximal central port on the Szabo box trainer. Insert a 5mm lateral port (left or right) half way down the Szabo box trainer.

Place the coloured cylinders in a circular style in a vertical upright position around the " +the academy..." sign on the LASTT model. There will be 2 cylinders of each colour in case one is dropped out of view. Trainee is expected to transfer only one cylinder of each colour to their corresponding nails.

On the LASTT model there are 6 coloured discs (blue, red, yellow, green, black and white) and a pin is located next to each coloured disc.

Request the trainee to read the instructions and then show them the demonstration video.

Check trainee's understanding of the task.

The trainee is expected to pick **one** coloured cylinder using grasping forceps (Maryland) in their dominant hand and then place this cylinder on its corresponding coloured nail on the wooden model.

If they drop a cylinder, they can use the second cylinder of the same colour or could re-grasp the fallen one, as long as it remains in endoscopic view.

The trainee is expected to insert the 0 degrees camera and the timer starts when the grasper is inserted through the lateral port and it can be seen in endoscopic view on the screen.

A total time of 3 minutes is allowed for this task. Record the time taken for trainee to transfer 6 cylinders if task completed within 3 minutes. If 3 minutes are exceeded then record the number of cylinders correctly transferred, i.e. 4 cylinders. Also record the number of time a cylinder is grasped and dropped.

Now change the inserts for round 2 using sequence 2 for this task and repeat above. Record the same data as above before proceeding to round 3 using sequence 3. Once this round is completed, record the above data and move the trainee on to task 3.

This task will be repeated 3 times with 3 different colour sequences.

Exercise 3: Bi-manual Coordination

The aim of this exercise is to evaluate trainee's ability to handle two forceps simultaneously with their dominant and non-dominant hands. As the facilitator you will navigate the camera for them and give them an optimal position or as per the trainee's instructions.

The LASTT model stays in position as per task 1 and 2.

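### Facilitators influence the task 1 and task 3 times, but the protocol neither balances them across specialties nor names them among the recorded data

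*Protocol*

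**What the plan says.** **Task 1.** The Task 1 section states that before the trainee goes on, "the facilitator needs to confirm that they are happy with the identification and placement of the small character". Appendix 13 words the test as "If you approve that the entirety or boundaries of the small character is placed in the circle on the screen". The round ends when the fourteenth target is found.

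**Task 2.** The trainee works the grasper "whilst using NDH to drive the camera", so no facilitator handles the camera.

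**Task 3.** Appendix 13, Exercise 3 says: "As the facilitator you will navigate the camera for them and give them an optimal position", or as the trainee directs. The Task 3 section has the facilitator insert the camera and centre the targets on the screen.

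**Task 4.** The facilitator holds the camera, again in an optimal position or as the trainee directs. Pad quality is scored afterwards by two independent assessors.

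**Pairing.** Appendix 13 says: "An assessor will be allocated to each trainee". It gives no rule for the allocation. Under Risks, burdens and benefits, a request for a change is accepted without a reason: "If they want to have a different facilitator because they may know or feel uncomfortable with them".

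**Recording.** The Task 1 section has the facilitator record the trainee's study number and the time. The Appendix 8 tables have columns for time, targets or objects, penalties and drops, and none for the facilitator.

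**Outcomes.** The primary outcome for tasks 1 to 3 is built on completion time averaged over three rounds, with counts where a round is incomplete. The task 4 entry lists sutures, correct knots and trauma under a 15-minute cap.

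**The concern.** The main text speaks of a facilitator and Appendix 13 of an assessor. Appendix 13 addresses the assessor as the facilitator, so I read them as one person. That person keeps the stopwatch, decides when a task 1 target counts, and controls the view in task 3. Two facilitators could therefore produce different times from trainees of equal skill.

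The comparison of 20 general surgery with 20 O&G trainees is not randomised, so nothing in the design evens out who is paired with whom. If one specialty happened to meet slower approvers or less steady camera holders more often, part of the difference in times would belong to the facilitators. If the pairing happened to be even, the variation would still add noise to cells of 10 trainees. The protocol collects trainee characteristics in Appendix 6 because they may confound, but it does not list this one. An analysis plan can adjust for facilitator only if the pairing has been kept.

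**Working it through.** The protocol gives no figure for facilitator variation, so there is nothing to reproduce. The check is a reading of the task procedures plus one labelled illustration.

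**1. Where the facilitator enters the outcome**

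| Task | Facilitator's part during timing | Outcome exposed |
|---|---|---|
| 1 | approves each target before the next | mean time, and the penalty count |
| 2 | none on camera | no camera effect |
| 3 | positions the camera | mean time, or pins placed |
| 4 | positions the camera | time and number completed only |

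**2. How tightly the part is specified.** In task 1 the main text asks for the character to be placed in the circle and read aloud. Appendix 13 mentions placement only, and accepts either the 'entirety' or the 'boundaries' of the character. In task 3 the main text reads as one centred view, while Appendix 13 has the facilitator navigate or follow the trainee. Some discretion remains in both.

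**3. Number of releases in task 1.** There are 14 targets, and finding the last one completes the round. Approvals that release a further target = 14 − 1 = 13.

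**4. Illustration.** Let d be the difference in approval time per target between two facilitators. The documents give no value, so I assume 0.5 to 2 seconds. The ideal time of 2 minutes 30 seconds is 150 seconds.

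- Gap per round = 13 × d
- d = 0.5 s: 13 × 0.5 = 6.5 s; 6.5 / 150 = 4.3%
- d = 1 s: 13 × 1 = 13 s; 13 / 150 = 8.7%
- d = 2 s: 13 × 2 = 26 s; 26 / 150 = 17.3%

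Even 26 s is less than one 30-second penalty step, but it can carry a trainee near a boundary across it and cost one target.

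**5. Averaging does not remove it.** If the same facilitator takes a trainee through all three rounds, the shift in the mean is (13d + 13d + 13d) / 3 = 13d.

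**6. From facilitator gap to specialty difference.** With two facilitators, let p_GS and p_OG be the share of each specialty seen by the slower one. The shift in the specialty contrast is 13d × (p_GS − p_OG). It is zero when the shares are equal. It reaches the full 6.5 to 26 s only if one specialty sees only the slow facilitator and the other only the fast one. The protocol does not determine these shares, so the bias cannot be computed.

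**The case against.** Several points against the concern stand.

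- **Clustering by specialty is not shown.** A reader might infer that trainees' choice of dates sorts the specialties onto different facilitators. Both specialties choose from the same six days, and nothing says that allocation follows specialty. The swap clause could reduce familiarity bias as easily as it creates imbalance. Confounding is possible, not demonstrated.
- **Irrecoverability is not shown.** A reader might infer from Appendix 8 that the pairing is lost for good. The tables as extracted also lack the trainee's study number, which the text says is used on the evaluation sheets, so identifying fields may sit outside them. An allocation list may also exist. What can be said is that no facilitator identifier is named among the recorded data.
- **The seconds are assumed.** They describe two facilitators, not two specialties. Counting 14 releases would overstate the gap, because the last target ends the round.
- **Tasks 3 and 4 are easily overstated.** The trainee may direct the camera, and task 4 quality is scored independently afterwards.
- **Controls exist.** These are standardised instructions and videos, no performance feedback, the same three sequences for everyone, and specified model and port placement.

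It can also be said that a rota is operational detail and that a facilitator-adjusted analysis belongs in an analysis plan. The second part is fair, and the absence of such an analysis here is not the fault. The first part does not dispose of the point, because pairing and its recording are fixed on the test day and no later analysis plan can supply them. Nor do the listed controls standardise approval speed or camera handling.

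**Conclusion.** The concern holds in a limited form. The facilitator affects the timed outcomes in tasks 1 and 3, and task 4 less directly. The protocol leaves the pairing unbalanced over specialty and grade, open to change on request, and without a named identifier. A facilitator effect could be confounded with specialty or add noise, and could be hard to separate afterwards. The protocol does not support a claim that the comparison is biased, or in which direction.

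The only size available is conditional: 6.5 to 26 seconds per task 1 round, 4% to 17% of the ideal time, between two facilitators who differ by an assumed 0.5 to 2 seconds per approval. No comparable figure can be given for camera handling. This is a worthwhile low-cost improvement in conduct, not a fatal fault.

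**What to change.** - Add a facilitator ID to each Appendix 8 sheet, and log every change made on request.
- Assign facilitators so that each sees both specialties and, as far as bookings allow, both grade bands.
- Replace the two task 1 wordings with one written approval criterion that says whether the whole character or only its boundaries must lie in the circle.
- Run a facilitator-adjusted sensitivity analysis for tasks 1 and 3.
- If testing has already taken place, reconstruct the pairings from any list that was kept and report what could not be recovered as a limitation.

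The cost is a form field and some effort on the rota. Balance will be only approximate, because trainees choose their dates and may ask for another facilitator. With about 40 trainees the facilitator variance will be estimated imprecisely, so the adjusted result should be read as a check and not as a replacement for the main comparison.
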